4.1 Overall Design

The design of the study is summarized in [Table 4.1](#).

Table 4.1: Overall design

Type of design	3-arm study with either concomitant or single administration of Fluzone High-Dose Quadrivalent vaccine and Moderna COVID-19 Vaccine
Phase	II
Control method	Active-controlled (single administration versus coadministration)
Study population	Adults 65 years of age and older
Level and method of blinding	Open-label
Study intervention assignment method	Randomization
Number of participants	300 participants 65 years of age and older
Intervention groups	Participants will be randomly assigned to 1 of the 3 study groups in a 1:1:1 ratio, corresponding to i) concomitant administration of Fluzone High-Dose Quadrivalent vaccine and Moderna COVID-19 Vaccine, ii) administration of Fluzone High-Dose Quadrivalent vaccine alone, and iii) administration of Moderna COVID-19 Vaccine alone
Total duration of study participation	Approximately 180 days (6 months after vaccination) for all participants.
Countries	United States
Use of an Independent Data Monitoring Committee, Dose Escalation Committee, or similar review group	No

4.2 Scientific Rationale for Study Design

There is currently no data on the concomitant administration of high-dose quadrivalent influenza vaccine and mRNA based SARS-CoV-2 vaccines. Influenza vaccines, including Fluzone High-Dose Quadrivalent vaccine, are recommended in the national immunization program of several countries. Given the worldwide COVID-19 pandemic, many countries are currently implementing massive SARS-CoV-2 vaccination programs using one or more vaccines, including Moderna COVID-19 Vaccine. Therefore, the concomitant administration of both Fluzone High-Dose Quadrivalent vaccine and Moderna COVID-19 Vaccine is anticipated as immunization programs overlap.

Both vaccinations for the prevention of influenza and the prevention of COVID-19 disease are recommended in persons aged 65 years and older. While Fluzone High-Dose Quadrivalent vaccine is indicated for the prevention of influenza in population aged 65 years and older, Moderna COVID-19 Vaccine may be administered to adults aged 18 years and older.

The present study will investigate the safety and immunogenicity of Fluzone High-Dose Quadrivalent vaccine and a third/booster dose of Moderna COVID-19 Vaccine when administered concomitantly or singly in adults 65 years of age and older in the US.

4.3 Justification for Dose

A single dose of Fluzone High-Dose Quadrivalent vaccine is indicated for individuals 65 years of age and older to give protection against influenza.

So far, the safety and efficacy of Moderna COVID-19 Vaccine has been shown when the vaccine is administered as a course of 2 doses at least 28 days apart. However, repeated vaccination with a single dose of Moderna COVID-19 Vaccine (third or booster dose) is currently under evaluation in clinical studies and may be recommended. Although the Advisory Committee on Immunization Practices (ACIP) does not currently provide guidance for a booster (third) dose, adults 65 years of age and older are at the highest risk for COVID-19 and related complications and thus more likely to be prioritized in the event a third dose is recommended.

Therefore, participants in this study will be administered a dose of Fluzone High-Dose Quadrivalent vaccine and a dose of Moderna COVID-19 Vaccine either concomitantly or singly.

4.4 End of Study Definition

A participant is considered to have completed the Active Phase if he/she completed V02. Likewise, a participant is considered to have completed the 6-month safety follow-up if he/she completed the 6-month telephone contact planned in the SoA.

The end of the study is defined as the date of the last contact of the last participant in the study.

However, for periodic safety reports, the study is considered completed when the clinical study report is finalized.

5 Study Population

Prospective approval of protocol deviations to recruitment and enrollment criteria, also known as protocol waivers or exemptions, is not permitted.

5.1 Inclusion Criteria

Participants are eligible for the study only if all of the following criteria are met:

Age

I01: Aged ≥ 65 years of age on the day of inclusion^a.

Type of participant and disease characteristics

^a “ ≥ 65 years” means from the day of the 65th birthday onwards.

- I02: In good health or with underlying medical condition(s) that are judged to be stable by the Investigator. A stable medical condition is defined as disease not requiring significant change in therapy or hospitalization for worsening disease during the 3 months before enrollment.
- I03: Participants who previously received 2 injections of Moderna COVID-19 Vaccine with the second dose received at least 5 months before V01^a.

Informed Consent

- I04: Informed consent form has been signed and dated.

Other Inclusions

- I05: Able to attend all scheduled visits and to comply with all study procedures.

5.2 Exclusion Criteria

Participants are not eligible for the study if any of the following criteria are met:

Medical conditions

- E01: Known or suspected congenital or acquired immunodeficiency; or receipt of immunosuppressive therapy, such as anti-cancer chemotherapy or radiation therapy, within the preceding 6 months; or long-term systemic corticosteroid therapy (prednisone or equivalent for more than 2 consecutive weeks within the 3 months preceding planned inclusion)**
- E02: Known systemic hypersensitivity to any of the study intervention components, or history of a life-threatening reaction to the study interventions used in the study or to a product containing any of the same substances^b
- E03: Previous dermal filler injection (either lips or face fillers)
- E04: Thrombocytopenia, contraindicating IM injection**
- E05: Bleeding disorder, or receipt of anticoagulants in the 3 weeks preceding inclusion, contraindicating IM vaccination.
- E06: Chronic illness that, in the opinion of the Investigator, is at a stage where it might interfere with study conduct or completion.^c
- E07: Moderate or severe acute illness/infection (according to Investigator judgment) on the day of study intervention administration or febrile illness (temperature $\geq 100.4^{\circ}\text{F}$ [38.0°C]). A

^a Confirmation of receipt of the 2-dose schedule of Moderna COVID-19 Vaccine will be documented by capturing the date and lot number of the second Moderna COVID-19 Vaccine injection in source document.

^b The components of study interventions are listed in the Prescribing Information for the Fluzone High-Dose Quadrivalent vaccine and in the Investigator's Brochure for the Moderna COVID-19 Vaccine.

^c Chronic illness may include, but is not limited to, cardiac disorders, renal disorders, autoimmune disorders, diabetes, psychomotor diseases, and known congenital or genetic diseases.

prospective participant should not be included in the study until the condition has resolved or the febrile event has subsided

- E08: Alcohol, prescription drug, or substance abuse that, in the opinion of the Investigator, might interfere with the study conduct or completion
- E09: History of serious adverse reaction to any influenza or COVID-19 vaccines
- E10: Personal history of Guillain-Barré syndrome (GBS)
- E11: Any condition that in the opinion of the Investigator would pose a health risk to the participant if enrolled or could interfere with the evaluation of the vaccine
- E12:** Personal history of clinically significant developmental delay (at the discretion of the Investigator), neurologic disorder, or seizure disorder
- E13:** Known seropositivity for human immunodeficiency virus, hepatitis B, or hepatitis C

Prior/concomitant therapy

- E14:** Receipt of **any vaccine in the 4 weeks preceding the study intervention(s) administration or planned receipt of any vaccine in the period between V01 and 4 weeks following the study intervention(s) administration^a**
- E15: Receipt of blood-derived immune globulins, blood, or blood-derived products in the past 3 months

Prior/concurrent clinical study experience

- E16:** Participation at the time of study enrollment (or in the 30 days preceding the first study vaccination) or planned participation during the present study period in another clinical study investigating vaccine, drug, medical device, or medical procedure

Other exclusions

- E17: Deprived of freedom by an administrative or court order, or in an emergency setting, or hospitalized involuntarily
- E18: Identified as an Investigator or employee of the Investigator or study center with direct involvement in the proposed study, or identified as an immediate family member (ie, parent, spouse, natural or adopted child) of the Investigator or employee with direct involvement in the proposed study

5.3 Lifestyle Considerations

No other restrictions than the ones listed in the exclusion criteria or in the contraindications for subsequent vaccinations are required.

^a It is to be noted that vaccination with Fluzone High-Dose Quadrivalent vaccine offered to Group 3 participants at the end of the Active Phase (V02) will not be considered by the Sponsor as meeting exclusion criterion #14.

5.4 Screen Failures

Screen failures are defined as participants who consent to participate in the clinical study but are not subsequently randomly assigned to study intervention. Screening information is recorded in the source documents.

Individuals who do not meet the criteria for participation in this study (screen failure) cannot be rescreened.

5.5 Criteria for Temporarily Delaying Enrollment, Randomization, Administration of Study Intervention, or Blood Draws

Not applicable.

6 Study Interventions and Concomitant Therapy

Study intervention is defined as any investigational intervention(s), marketed product(s), placebo, or medical device(s) intended to be administered to a study participant according to the study protocol.

Note: Vaccines or products administered outside of study protocol are not considered as study interventions and are reported in the CRF as reportable medications (see [Section 6.8](#)). Study procedures (eg, blood sampling) are also not considered as study interventions.

6.1 Study Interventions Administered

Study interventions are described in [Table 6.1](#).

Table 6.1: Identity of study interventions

Intervention Name	Fluzone High-Dose Quadrivalent vaccine, 2021-2022 formulation	Moderna COVID-19 Vaccine (mRNA-1273 vaccine)
Use	Experimental conditions or Other (as indicated in the prescribing material)	Experimental conditions or Other (as indicated in the prescribing material)
Type	Vaccine	Vaccine
IMP and NIMP	IMP	IMP
Dose Formulation	Sterile suspension for injection in a pre-filled syringe	Sterile suspension (white to off-white) in multidose vial
Unit Dose Strengths	60 mcg of HA of each of the following strains per dose: • A/Victoria/2570/2019 IVR-215 (H1N1)	Each dose will contain 100 mcg of mRNA (formulated in SM-102 lipid nanoparticles)

	
 • A/Tasmania/503/2020 IVR-221 (an A/Cambodia/e0826360/2020-like virus) (H3N2) • B/Phuket/3073/2013 (B Yamagata lineage) • B/Washington/02/2019 (B Victoria lineage) 	
Excipients/Diluent	Octylphenol ethoxylate (Triton X-100), sodium phosphate-buffered isotonic sodium chloride solution	Lipid SM-102 Cholesterol 1,2-distearoyl-sn-glycero-3-phosphocholine (DSPC) 1,2-Dimyristoyl-rac-glycero-3-methoxypolyethylene glycol-2000 (PEG2000 DMG) Tromethamol Tromethamol hydrochloride Acetic acid Sodium acetate trihydrate Sucrose Water for injections
Dosage Level	0.7 mL per dose	0.5 mL per dose
Number of Doses/Dosing Interval	One injection at V1 (D01) alone or co-administered with Moderna COVID-19 Vaccine	One injection at V1 (D01) alone or co-administered with Fluzone High-Dose Quadrivalent vaccine
Route of Administration	IM injection	IM injection
Site of Administration	Deltoid muscle in the upper arm	Deltoid muscle in the upper arm
Injection Site Side for Concomitant Administration	Injection sites should be on opposite sides for participants enrolled in Group 1	
Sourcing	Provided by the Sponsor	Provided by the US Government
Packaging and Labeling	Fluzone High-Dose Quadrivalent vaccine and Moderna COVID-19 Vaccine will be supplied with their manufacturer's commercial labeling and packaging.	
Batch Number	TBD	TBD
Storage Conditions	2 to 8°C	2 to 8°C (up to 30 days) -25 to -15°C (long term)

Study arms and associated study intervention are summarized in [Table 6.2](#).

Table 6.2: Arms and Associated Study Interventions

Arm name	Group 1	Group 2	Group 3
Associated study interventions	Concomitant administration of Fluzone High-Dose Quadrivalent vaccine and Moderna COVID-19 Vaccine	Fluzone High-Dose Quadrivalent vaccine alone	Moderna COVID-19 Vaccine alone

6.2 Preparation/Handling/Storage/Accountability

Detailed guidance and information are provided in the Operating Guidelines.

- 1) The investigator or designee must confirm appropriate temperature conditions have been maintained during transit for all study intervention received and any discrepancies are reported and resolved before use of the study intervention.
- 2) Only participants enrolled in the study may receive study intervention and only authorized site staff may supply or administer study intervention. All study intervention must be stored in a secure, environmentally controlled, and monitored (manual or automated) area in accordance with the labeled storage conditions with access limited to the investigator and authorized site staff.
- 3) The investigator, institution, or the head of the medical institution (where applicable) is responsible for study intervention accountability, reconciliation, and record maintenance (ie, receipt, reconciliation, and final disposition records).
- 4) Further guidance and information for the final disposition of unused study interventions are provided in the Operating Guidelines.

6.3 Measures to Minimize Bias: Randomization and Blinding

6.3.1 Randomization and Allocation Procedures

Participants will be randomized in a 1:1:1 ratio into Group 1, Group 2, and Group 3, using a permuted block method with stratification by site and by age group (< 75 years and \geq 75 years).

The full detailed procedures for randomization are described in the Operating Guidelines.

Participant numbers will be 12 digits long, with a 3-digit country identifier, a 4-digit study center identifier, and a 5-digit participant identifier. The 5-digit participant identifier will correspond to the chronological order of enrollment in the center within each stratum. For example, Participant 8400001-00001 is the first participant enrolled in Center Number 1 (in the US) and Participant 8400002-00002 is the second participant enrolled in Center Number 2 (in the US), within the < 75 years stratum.

Participant numbers should not be reassigned for any reason. The randomization codes will be kept securely in an internal system.

The Biostatistics platform of the Sponsor will provide randomization lists that will be printed as scratchable lists. These lists will mention the randomization order of the participant and the corresponding study group covered by a silver-colored patch. The Investigator will scratch off the list to know the study group. Once scratched, each randomization line will be dated and signed by the Investigator or the sub-investigator in charge of administering the study intervention(s).

Each participant will be vaccinated with the study intervention(s) corresponding to the group mentioned on the randomization list. If the dose initially taken for the vaccination is broken or cannot be used, the Investigator will take another dose of the same study intervention

6.3.2 Blinding and Code-breaking Procedures

Code-breaking procedures are not applicable for this open-label study. However, the laboratories conducting immunogenicity assays will be blinded to individual participant assignment or treatment.

6.4 Study Intervention Compliance

The following measures will ensure that the study intervention is administered as planned (see [Table 6.1](#)), and that any non-compliance is documented so that it can be accounted for in the data analyses:

- All study interventions will be administered by qualified and trained study personnel
- The person in charge of study intervention management at the site will maintain accountability records of study intervention delivery to the study site, study intervention inventory at the site, dose(s) given to each participant, and unused or wasted doses

6.5 Dose Modification

Not applicable.

6.6 Continued Access to Study Intervention After the End of the Study

Not applicable.

6.7 Treatment of Overdose

Since the study intervention is administered by a health care professional, it is unlikely that overdose by injection occurs.

However, in the event of an overdose, the investigator should:

- 1) Contact the RMO immediately.
- 2) Evaluate the participant to determine, in consultation with the RMO, whether study intervention should be interrupted

- 3) Closely monitor the participant for any AE/SAE.
- 4) Document the quantity of the excess of the overdose in the source documents.

6.8 Concomitant Therapy

Reportable medications include medications that may affect the interpretation of safety data (eg, an antipyretic or analgesic that could have reduced the intensity or frequency of an adverse event) or may interfere with the development or measurement of the immune response (eg, the use of immune-suppressors, immune-modulators, or some antibiotics that can affect certain bioassays). Some medications such as steroids can affect both the evaluation of the safety and the immune response to a vaccine.

This may include medications of interest that were started prior to the day of vaccination, and even stopped prior to enrollment if there is a reasonable possibility that they may have an impact on safety and / or immune assessment during study participation.

The following reportable medications are defined:

- medications impacting or that may have an impact on the evaluation of the safety (eg, antipyretics, analgesics, and non-steroidal anti-inflammatory drugs [NSAIDs], systemic steroids/corticosteroids)

Note: Topical analgesics should NOT be applied at the injection site of study intervention; however, if they are applied inadvertently, they should be recorded.

- medications impacting or that may have an impact on the immune response (eg, other vaccines, blood products, antibiotic classes that may interfere with bioassays used by Sanofi Pasteur laboratory or other testing laboratories, systemic steroids/corticosteroids, immune-suppressors, immune-modulators with immunosuppressive properties, anti-proliferative drugs such as DNA synthesis inhibitors)
- medications impacting or that may have an impact on both the safety and the immune response (eg, systemic steroids/corticosteroids)

Reportable medications will be collected in the CRF until the end of the solicited and unsolicited follow-up period.

Dosage and administration route, homeopathic medication, topical and inhaled steroids, as well as topical, ophthalmic, and ear treatments will not be recorded (except topical analgesics applied at the injection site of study intervention).

Medications given in response to an AE will be captured in the “Action Taken” section of the AE CRF only. No details will be recorded in the concomitant medication Form of the CRF unless the medication(s) received belongs to one of the pre-listed categories. Medications will be coded.

6.8.1 Rescue Medicine

Appropriate medical equipment and emergency medications, including epinephrine (1:1000), must be available at the study site in the event of an anaphylactic, vasovagal, or other immediate allergic reaction.

7 Discontinuation of Study Intervention and Participant Discontinuation/Withdrawal

7.1 Discontinuation of Study Intervention

Not applicable as there is only one vaccination visit.

7.2 Participant Discontinuation/Withdrawal from the Study

- A participant may withdraw from the study at any time at his/her own request, or may be withdrawn at any time at the discretion of the investigator for safety, behavioral, or compliance reasons. This is expected to be uncommon.
- The reason for withdrawal should be clearly documented in the source documents and in the CRF: Adverse Event, Lost to Follow-up, Protocol Deviation, or Withdrawal by Participant.
- The participant will be permanently discontinued from the study at that time.
- If the participant withdraws consent for disclosure of future information, the Sponsor may retain and continue to use any data collected before such a withdrawal of consent.
- If a participant withdraws consent, he/she may request destruction of any biological samples taken (unless local law requires not to destroy them), and the investigator must document this in the site study records.
- Withdrawn participants will not be replaced.

Follow-up of Discontinuations

For participants who have prematurely terminated the study, the site should attempt to contact them and complete all scheduled safety follow-ups, except if they specified that they do not want to be contacted again and it is documented in the source document.

For participants where the reason for early termination is lost to follow-up, the site will not attempt to obtain further safety information. See [Section 7.3](#) for definition of “lost to follow-up”.

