7.3 Lost to Follow-up

A participant will be considered lost to follow-up if he or she repeatedly fails to return for scheduled visits and is unable to be contacted by the study site.

The following actions must be taken if a participant fails to return to the site for a required study visit or cannot be contacted as planned in the SoA:

- The site must attempt to contact the participant and reschedule the missed visit as soon as possible and counsel the participant on the importance of maintaining the assigned visit schedule and ascertain whether or not the participant wishes to and/or should continue in the study.

- Before a participant is deemed lost to follow-up, the investigator or designee must make every effort to regain contact with the participant (where possible, 3 telephone calls and, if necessary, a certified letter to the participant's last known mailing address or local equivalent methods). These contact attempts should be documented in the participant's medical record.
- Should the participant continue to be unreachable, he/she will be considered lost to follow-up.

Discontinuation of specific sites or of the study as a whole are handled as part of [Appendix 10.1](#).

8 Study Assessments and Procedures

- Study procedures and their timing are summarized in the SoA. Protocol waivers or exemptions are not allowed.
- Immediate safety concerns should be discussed with the Sponsor immediately upon occurrence or awareness to determine if the participant should continue or discontinue study intervention.
- Adherence to the study design requirements, including those specified in the SoA, is essential and required for study conduct.
- All screening evaluations must be completed and reviewed to confirm that potential participants meet all eligibility criteria. The investigator will maintain a screening log to record details of all participants screened and to confirm eligibility or record reasons for screening failure, as applicable.

Blood samples will be collected as described in the SoA table ([Section 1.3](#)).

The maximum amount of blood collected from each participant over the duration of the study, including any extra assessments that may be required, will not exceed 40 mL, see [Table 8.1](#). Repeat or unscheduled samples may be taken for safety reasons or for technical issues with the samples.

Table 8.1: Blood sampling volume (mL) per visit

Visit Number (V) Trial Timelines (Days) Time Windows (Days)	V01 D01	V02 D22 [+3 days]

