8.3.1 Time Period and Frequency for Collecting AE and SAE Information

Immediate Post-vaccination Observation Period

Participants will be kept under observation for 30 minutes after vaccination to ensure their safety. The post-vaccination observation should be documented in the source document.

Reactogenicity

Solicited injection site reactions will be collected from the day of vaccination (D01) until 7 days after vaccination (D08).

Solicited systemic reactions will be collected from the day of vaccination (D01) until 7 days after vaccination (D08).

The solicited injection site reactions and systemic reactions that are pre-listed in the diary cards and CRF, together with the intensity scales, are presented in [Appendix 10.2.5.1.1](#).

Unsolicited Non-serious Adverse Events

Unsolicited non-serious adverse events will be collected from the day of vaccination (D01) until 21 days after vaccination (D22).

The intensity grading scale for unsolicited non-serious adverse events is presented in [Appendix 10.2.5.1.2](#).

Medically Attended Adverse Events (MAAEs)

MAAEs will be collected from D01 to D181.

Adverse Events of Special Interest (AESIs)

AESIs will be collected from D01 to D181.

See [Section 8.3.6](#) for the list of AESIs.

SAEs

Information on SAEs will be collected and assessed throughout the study, from the time of vaccination (D01) until 6 months after vaccination (D181). However, before the first study intervention administration, only SAEs related to study procedures are to be collected in the case report form (CRF).

All SAEs will be recorded and reported to the Sponsor or designee immediately and under no circumstance should this exceed 24 hours, as indicated in [Appendix 10.2](#). The investigator will submit any updated SAE data to the Sponsor within 24 hours of it being available.

Investigators are not obligated to actively seek information on AEs or SAEs after conclusion of the study participation. However, if the investigator learns of any SAE, including a death, at any time after a participant has been discharged from the study, and he/she considers the event to be reasonably related to the study intervention or study participation, the investigator must promptly notify the Sponsor.

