4.2.4 Derived Other Variables

4.2.4.1 Age for Demographics

The age of a participant in the study will be the calendar age in years at the time of inclusion, as collected in the eCRF.

For randomization stratification and subgroup analyses, the 2 following classes of age will be used: < 75 years and ≥ 75 years.

5 Changes in the Conduct of the Trial or Planned Analyses

This section summarizes major changes in the SAP amendment.

Table 5.1: Major statistical changes in SAP amendment

Amendment Number	Approval Date	Changes	Rationale
Amendment 1 (SAP v2.0)		Addition of 6-month f-up analysis	Protocol Amendment 2

6 Supporting Documentation

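### Once a participant is classed as lost to follow-up, which can happen soon after a missed D22 visit, sites may not attempt the D181 safety call, so 6-month SAE, AESI and MAAE rates can be understated

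*Protocol*

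**What the plan says.** Protocol Section 7.2 treats two kinds of early terminator differently. In general, "the site should attempt to contact them and complete all scheduled safety follow-ups, except if they specified that they do not want to be contacted". For those whose reason is loss to follow-up the instruction is the reverse: "For participants where the reason for early termination is lost to follow-up, the site will not attempt to obtain further safety information".

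Section 7.3 says who may be given that status: a participant who "repeatedly fails to return for scheduled visits and is unable to be contacted by the study site". Before that, "The site must attempt to contact the participant and reschedule the missed visit as soon as possible", and the investigator or designee "must make every effort to regain contact with the participant (where possible, 3 telephone calls and, if necessary, a certified letter" or a local equivalent. If the participant is still unreachable, the status applies. No earliest study day is given, and no later attempt is required.

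The Schedule of Activities (Protocol Table 1.1) has one return visit after vaccination, V02 at D22, and two calls: TC1 at D08 and TC2 at D181 (window +14 days). Section 8.3.2 makes the telephone interview the method of 6-month ascertainment. SAEs, AESIs and MAAEs up to 6 months are endpoints (Protocol Table 3.1; SAP Table 2.1).

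The SAP places in the SafAS everyone who received at least one dose (Section 3.3), generally replaces no missing safety data (Section 3.4.4.1), and tabulates these events from D22 to 180 days and within 180 days (Sections 4.2.1.2.6 to 4.2.1.2.8).

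**The concern.** The rule ends active ascertainment well before the endpoint window closes. A participant unreachable near D22 may be reachable at D181, but the site is told not to try. Participants who leave for an adverse event, a protocol deviation or withdrawal are still followed to D181 unless they refuse contact. The gap is therefore confined to one group, and the instruction itself creates it.

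At stake is the completeness of the 6-month safety description. A SafAS member with no D181 contact and no earlier report contributes to the denominator and not to the numerator, so the error can only lower the rate. The plan does not say how 6-month rates treat people without TC2, and it plans no display of how many there are.

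**Working it through.** **1. Timing.** V02 is V01 + 21 days and TC2 is V01 + 180 days. The gap is 180 − 21 = 159 days, about five months, with no planned contact between them. With only one return visit, a missed and rescheduled V02 followed by failed calls and a letter can complete the Section 7.3 steps.

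**2. Other routes to the data.** Events may be reported at any time during the study, so anything reported before loss counts. After discharge, Protocol Section 8.3.1 requires notification only of SAEs that the investigator happens to learn of and considers reasonably related. It does not oblige investigators to seek information. Unrelated SAEs, non-serious AESIs and MAAEs have no such route.

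**3. The plan's own figure.** Protocol Section 9.2 assumes 5% drop-out from about 100 per group: 100 × (1 − 0.05) = 95, as stated. Over three groups that is 3 × 5 = 15 drop-outs. The documents do not say what share would be lost to follow-up.

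**4. Shortfall from loss.** Let L be the number lost per 100, p the event risk in those followed, and RR the relative risk in those lost, with no event recorded before loss.

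- True rate = [(100 − L)p + L·p·RR]/100
- Recorded rate on the SafAS = (100 − L)p/100
- Shortfall = L·p·RR/100

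The values of p and RR are assumptions; the documents give neither. With L = 5, meaning every drop-out is lost, the shortfall in percentage points is:

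| p | RR = 1 | RR = 2 | RR = 4 |
|---|---|---|---|
| 2% | 0.10 | 0.20 | 0.40 |
| 5% | 0.25 | 0.50 | 1.00 |
| 20% | 1.00 | 2.00 | 4.00 |

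With L = 2 the same grid runs from 0.04 to 1.60 points. The ceiling is 5/100 = 5 points, if all five had an unrecorded event.

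**5. The part due to the rule.** If a fraction f of the missed events would be recovered by a later call, the rule accounts for f × L·p·RR/100. Nothing in the documents fixes f. For example, with L = 5, p = 5% and RR = 2, the rule accounts for anything from 0 (f = 0) to 0.50 points (f = 1).

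**6. Scale.** The exact 95% interval is 1.6% to 11.3% for 5/100 and 0% to 3.6% for 0/100. Sampling error exceeds most of the table, but the interval does not show this shortfall and the shortfall has one direction.

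**7. Denominator.** If rates were taken only on those contacted, the shortfall at RR = 1 would be zero. At L = 5, p = 5%, RR = 4 the true rate is (95 × 0.05 + 5 × 0.20)/100 = 5.75%. The contacted-only rate is 5.00%, short by 0.75 points, against 1.00 on the SafAS. Knowing TC2 completion therefore helps in reading the rates.

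**The case against.** The best defence is that the rule applies only to people already shown to be unreachable. Disappearing before V02 does not by itself end contact, because Section 7.3 puts rescheduling, calls and a letter first. All other early terminators remain under scheduled follow-up. A further call may fail as the earlier ones did, the study is descriptive with no hypothesis test, and the numbers are small. All of this stands and limits the size. It does not explain why one attempt at the endpoint date should be forbidden.

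Four stronger readings are tempting, and the documents do not support them.

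- **That those lost are the likeliest to have had an event.** In adults aged 65 and older, illness is a plausible cause of a missed visit, but nothing in the plan says so. The shortfall does not need it: at RR = 1 the SafAS rate is still too low.
- **That loss will differ by arm and distort the comparison with single administration.** This is possible in an open-label trial, but it is not stated.
- **That the 5% is a lost-to-follow-up rate.** It is drop-out from all causes, and Section 7.2 lists four reasons for withdrawal.
- **That the sentence is left over from a study ending at D22.** SAP Section 5 records "Addition of 6-month f-up analysis" under Protocol Amendment 2. That shows when the analysis was added to the SAP, not why the protocol sentence was written.

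**Conclusion.** The point holds in a narrow form. Section 7.2 stops active safety follow-up for anyone classed as lost, the status can be assigned about five months before D181, and no final attempt is required. The 6-month SAE, AESI and MAAE rates on the SafAS can be understated as a result.

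The size is unknown and probably small: at most 5 points per arm under the extreme assumptions in the working, and well under that for most plausible inputs. The rule is responsible only for the recoverable part. The conclusion assumes that 6-month rates use the full SafAS as denominator, which follows from the SafAS definition because the SAP gives no other rule for these events. This is a cheap improvement to ascertainment and does not threaten the study's conclusions.

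**What to change.** Replace the sentence in Protocol Section 7.2 with:

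> For vaccinated participants classed as lost to follow-up before D181, the site will still make one further attempt at the D181 contact (TC2) to collect any SAE, AESI or MAAE, unless the participant has asked not to be contacted again.

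The attempt should use only contact details already held and consented. The protocol provides no alternate-contact or physician route, and adding one could require a new consent step. In the SAP, add TC2 completion by group alongside the 6-month rates.

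Cost: one amended sentence, with the ethics approval that Protocol Section 10.1.1 requires for any amendment, one extra display, and at most about 15 call attempts (5% of 300), some of which will fail. No new visit, sample or staff is needed.
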